6.2 Pre-Operative TASOX

6.2.1 TAS102

Each treatment cycle will be 14 days in duration. TAS-102 dosage is calculated according to body surface area.

One treatment cycle consists of the following:

Days 1-5: TAS-102 (35 mg/m²/dose) orally BID

Days 6-14: Rest

Repeat for a total of 6 cycles.

Study medication should be taken on Days 1-5. If doses are missed or held on those days, the patient should not make up for missed doses.

TAS-102 should be taken with a glass of water within 1 hour after completion of morning and evening meals.

6.2.2 Number of Tablets per Dose

Tablet calculation is presented in Table 2. TAS-102 should only be given on Days 1 through 5 of each cycle even if doses are missed or held for any reason during Days 1 through 5.

		Dosage in		Tablets	per dose
TAS-102 Dose (2x daily)	BSA (m ²)	mg (2x daily)	Total daily dose (mg)	15 mg	20 mg
35 mg/m ²	< 1.07	35	70	1	1

Table 2:TAS-102 Tablets per Dose

		Dosage in		Tablets	per dose
TAS-102 Dose (2x daily)	BSA (m ²)	mg (2x daily)	Total daily dose (mg)	15 mg	20 mg
	1.07 - 1.22	40	80	0	2
	1.23 - 1.37	45	90	3	0
	1.38 - 1.52	50	100	2	1
	1.53 - 1.68	55	110	1	2
	1.69 - 1.83	60	120	0	3
	1.84 - 1.98	65	130	3	1
	1.99 - 2.14	70	140	2	2
	2.15 - 2.29	75	150	1	3
	≥2.30	80	160	0	4

BSA=body surface area (calculate to 2 decimal places)

6.2.3 Instruction to Patients for Handling Study Medication

The patient must be instructed in the handling of study medication as follows:

- To store the study medication at room temperature
- To only remove from the study medication kit the amount of tablets needed at the time of dosing
- To wash their hands after handling study medication
- Not to remove doses in advance of the next scheduled dosing
- To make every effort to take doses on schedule
- To report any missed doses
- To take study medication within 1 hour after completing a meal (morning and evening meal) with a glass of water
- If the patient vomits after taking study medication, the patient should not take another dose
- To keep study medication in a safe place and out of reach of children
- To bring all used and unused study medication to the site at each visit

6.3 Oxaliplatin

Day 1: Oxaliplatin 85mg/m2 IV in 500 ml of D5W over 2 hours

Days 1-14: see TAS102 schedule. Repeat for a total of 6 cycles Oxaliplatin may be administered via peripheral or central IV, per institutional policy.

6.4 Surgical Therapy

Standard surgical therapy with a total mesorectal excision (TME) is to be done within 10 weeks of completion of cycle #6 of chemotherapy with TASOX with staging to be done within 8 weeks after day 14 of cycle 6.

Operative approach will be at the discretion of surgeon, and can include either laparoscopic (or robotic-assisted laparoscopic) or open anterior or low anterior resection with or without temporary fecal diversion. Preoperative antibiotics and bowel preparation are institution specific will be at the discretion of the operating surgeon. The mobilization of the proximal colon and splenic flexure may be performed by laparoscopic, laparoscopic-assisted, robotic-assisted or hand-assisted at the discretion of the surgeon to limit the incision to the lower abdomen. The pelvic dissection should include TME, division of inferior mesenteric vascular pedicle, transection of the specimen, and anastomosis. Anastomosis may be stapled or hand-sewn. Variation in technical approaches will be at the surgeon's discretion as they are impacted by the patient's body habitus, incisions, and tumor location.

Patients that achieve a complete or near complete Clinical Response (cCR or cCR), may choose to pursue a course of watch and wait with agreement of their treating surgeon. A thorough discussion is recommended with their surgeon concerning the risks and benefits of watch and wait and both they and their physician agree with the intended approach. Patients that pursue a course of watch and wait remain evaluable on study and will be classified as having a ypT0N0 response for the purposes of the NAR score if they do not proceed to TME surgery within 24 months of completing cycle 6, day 14.

Surgical Complications

Perioperative and postoperative complications will be collected and submitted; see Section 10.0.

Early complications (within 30 days)

Morbidity and mortality will be closely monitored and recorded using the study data forms with the following definitions:

- 1. Pulmonary, urinary tract, and intraabdominal infections will be defined by the need for antibiotic treatment and/or interventional radiology drainage.
- 2. Abdominal wound infections will be defined by the location, extent and severity (i.e. superficial vs. deep space infection) and the need for wound opening and/or surgical intervention. Urinary retention will be defined as the condition of urinary dysfunction that occurs for greater than 5 days following surgery or that requires intervention, including replacement of Foley catheter, surgery, etc
- 3. Perioperative hemorrhage requiring blood transfusion(s) or reoperation will be considered as a complication. Correction of preoperative anemia will not be included as a complication. The decision to transfuse will be made at the surgeon's discretion.

- 4. Any documented medical or anesthetic complications that result in patient disability or that requires intervention will be recorded.
- 5. Problems with healing, function or management of the ostomy that requires intervention or additional hospital stay will be considered complication and recorded.

7.0 RADIOLOGIC IMAGING

The primary interpretation of all imaging studies will occur at each site, and each site will make the initial determination for each patient as to:

- 1. Study eligibility
- 2. Initial MRI study adequacy
- 3. Baseline TNM status
- 4. Post-treatment T and N status

Estimated Radiographic T Stage (Using AJCC 8th Edition Definitions):

This should be estimated as T1, T2, or T3c/d (ie. T3c, >5 to 15 mm; T3d, >15 mm beyond muscularis propria). T4 tumors are ineligible. See APPENDIX I.

Estimated Radiographic N Stage:

For purposes of achieving consistent interpretation in this protocol:

Node positivity determination: Entry criteria nodes will be measured in short-axis diameter and for the purposes of study entry will be considered positive if 8mm in short axis.

Radiographic N2 status is estimated as: 4 or more nodes that measure 8mm or more in short-axis. Radiographic N1 status is estimated as: fewer than 4 lymph nodes that measure 8 mm or greater in short axis but 1 or more lymph nodes that measure 10 mm or greater.

Distance of the Tumor from the Mesorectal Fascia Reflection: patients with tumors with a distance of 1mm or less, or adherent to the mesorectal fascia reflection have threatened radial margins and are ineligible.

Presence of Distant Disease:

Nodal stations considered suspicious for metastatic disease (M1) for rectal cancer are: common iliac, external iliac and inguinal nodes.

8.0 SUGGESTED DOSAGE MODIFICATION BASED ON ADVERSE EVENTS

8.1 TASOX chemotherapy

8.1.1 TAS-102 Dose Reduction Levels

Study medication dose reductions in case of toxicity and number of tablets for each calculated BSA are described in Table 3. Patients are permitted dose reduction(s) to a minimum dose of 20 mg/m² bid(40 mg/m²/day) in 5 mg/m² steps.

Table 3: TAS-102 Dose Reduction Levels and Number of Tablets per Dose

TAS-102		Dosage in	Total	Tablets	per dose
Dose (2x	BSA	mg	daily		-
daily)	(m ²)	(2x daily)	dose (mg)	15 mg	20 mg
Level 1 Dose R	eduction: Fr	om 35 mg/m ² t	to 30 mg/m ²		
30 mg/m ²	< 1.09	30	60	2	0
	1.09 - 1.24	35	70	1	1
	1.25 - 1.39	40	80	0	2
	1.40 - 1.54	45	90	3	0
	1.55 - 1.69	50	100	2	1
	1.70 - 1.94	55	110	1	2
	1.95 - 2.09	60	120	0	3
	2.10 - 2.28	65	130	3	1
	≥ 2.29	70	140	2	2
Level 2 Dose R	eduction: Fr	om 30 mg/m ²	to 25 mg/m ²		
25 mg/m ²	< 1.10	25 ⁽¹⁾	50 ⁽¹⁾	2 (PM) ⁽¹⁾	1 (AM) ⁽¹⁾
	1.10 - 1.29	30	60	2	0
	1.30 - 1.49	35	70	1	1
	1.50 - 1.69	40	80	0	2
	1.70 - 1.89	45	90	3	0
	1.90 - 2.09	50	100	2	1
	2.10 - 2.29	55	110	1	2
	≥ 2.30	60	120	0	3
Level 3 Dose R	eduction: Fr	om 25 mg/m ²	to 20 mg/m ²		
20 mg/m ²	< 1.14	20	40	0	1
	1.14 - 1.34	25 ⁽¹⁾	50 ⁽¹⁾	2 (PM) ⁽¹⁾	1 (AM) ⁽¹⁾
	1.35 – 1.59	30	60	2	0
	1.60 - 1.94	35	70	1	1
	1.95 - 2.09	40	80	0	2
	2.10 - 2.34	45	90	3	0
	≥ 2.35	50	100	2	1

(1) At a total daily dose of 50 mg, patients should take 1 x 20-mg tablet in the morning and 2 x 15-mg tablets in the evening.

BSA=body surface area (calculate to 2 decimal places)

If dose modification fails to result in achieving minimal criteria to resume treatment, the Investigator should discontinue study medication.

Study medication should be discontinued if toxicities that require dose reduction recur after dose reduction to 20 mg/m^2 .

8.1.2 Oxaliplatin Dose Reduction Levels

Dose Modifications levels for oxaliplatin are listed in Table 6:

Table 4:Oxaliplatin dose modification levels				
Starting Dose Dose Level -1 Dose Level -2				
Oxaliplatin	85 mg/m2	65mg/m2	50mg/m2	

8.1.3 Dose Hold, Resumption and Modification in Response to Hematologic Toxicities

Criteria for dose HOLD and RESUMPTION in response to hematologic toxicities related to myelosuppression are described in Table 5 and 6, respectively.

For all patients with decreases in neutrophils and/or platelets noted in **Table 5**, the next cycle of study treatment should not be started until the resumption criteria in **Table 6** are met; these resumption criteria apply to the start of the next cycle for all patients regardless of whether or not the hold criteria were met. **Table 7** and **Table 8** summarize the relative dose reduction requirements for the TASOX regimen.

Table 5:TAS-102 and Oxaliplatin DOSE HOLD CRITERIA for Hematologic
Toxicities Related to Myelosuppression

	Hold Criteria		
Parameter	Conventional Units	SI Units	
Neutrophils	<1,000/mm ³	$<1.0 \times 10^{9}/L$	
Platelets	<50,000/mm ³	$<50 \times 10^{9}/L$	

SI=International System

Table 6:TAS-102 and Oxaliplatin RESUMPTION Criteria for Hematologic Toxicities
Related to Myelosuppression

	Resumption Criteria ⁽¹⁾		
Parameter	Conventional Units	SI Units	
Neutrophils	$\geq 1200/mm^3$	$\geq 1.2 \times 10^{9}/L$	
Platelets	\geq 75,000/mm ³	$\geq 75 \times 10^9/L$	

(1) These resumption criteria apply to the start of the next cycle for all patients regardless of whether or not the hold criteria were met.
CL Letometicael Sectors

SI=International System

Table 7:Combined dose MODIFICATION for TASOX regimen for Absolute
Neutrophil Counts (ANC).

Prior to cycle	ANC SI Units × 10 ⁹ /L	Dose level of subsequent cycles		
-If ANC is less than 1.2 within 3 days of day 1 of cycle, hold treatment. Perform weekly CBC, maximum of 4 times. -If ANC is greater than or equal to 1.2 within 4 weeks, proceed with treatment at the dose level noted across the lowest ANC result of the delayed weeks (s)		Oxaliplatin	TAS102	
	Greater than or equal to 1.2	Maintain dose level	Maintain dose level	
	1.0 to less than 1.2	Maintain dose level	Maintain dose level	
	0.5 to less than 1.0	Decrease 1 dose level	Maintain dose level	
	Less than 0.5	Decrease 1 dose level	Decrease 1 dose level	
-If ANC remains less than 1.2 after 4 weeks, discontinue treatment.				

Table 8:Combined dose modification for TASOX regimen for Absolute NeutrophilCounts (Plt).

Prior to cycle	Platelets SI Units	Dose level of subsequent cycles		
-If Plts are less than 75 within 3 days of day 1 of cycle, hold treatment. Perform	$\times 10^{9}/L$	Oxaliplatin	TAS102	
	Greater than or equal to 75	Maintain dose level	Maintain dose level	
weekly CBC, maximum of 4 times	50 to less than 75	Maintain dose level	Maintain dose level	
-If Plts are greater than or equal to 75 within 4 weeks, proceed with treatment at the dose level noted across the lowest Plt result of the delayed weeks(s)	10 to less than 50	Decrease 1 dose level	Maintain dose level	
	Less than 10	Decrease 1 dose level	Decrease 1 dose level	
If Plts remain less than 75 after 4 weeks, discontinue treatment.				

8.1.4 Dose Modification in Response to Febrile Neutropenia

In the event of febrile neutropenia:

- Interrupt dosing until toxicity resolves to treatment resumption level (Table 6).
- When resuming dosing, decrease the dose level by 1 dose level from the previous dose level for both oxaliplatin and TAS102 (as per Tables 3 and 4).

8.1.5 Dose Modification in Response to Non-Hematologic Toxicities

In Table 9 dose modifications for non-hematologic toxicities are defined. For grading of neurologic toxicity please see Table 10.

Table 9: TASOX Dose Modification Criteria for Non-hematologic Toxicities

Grade ^a	Dose Hold/Resumption within a 14-day Treatment Cycle	Dose Adjustment for Next Cycle			
Grade 1 or 2					
Any occurrence	Maintain treatment at the same dose level	None			
Grade 3 ⁽¹⁾ or Higher					
1 st , 2 nd , or 3 rd occurrence	Suspend treatment until Grade 0 or 1	Reduce by 1 dose level from the previous level			
4 th occurrence	Discontinue treatment	Discontinue treatment			

• ⁽¹⁾ Except for Grade 3 nausea and/or vomiting controlled by aggressive antiemetic therapy or diarrhea responsive to antidiarrheal medication.

Table 10: Oxaliplatin Neurotoxicity Definitions and Dose Modifications

Grade1	Paresthesias / dysesthesias of short duration			
	that resolve; do not interfere with function			
Grade 2	Paresthesias / dysesthesias interfering with			
	function, but not activities of daily living			
	(ADL)			
Grade 3	Paresthesias / dysesthesias with pain or with			
	functional impairment which interfere with			
	ADL			
Grade 4	Persistent paresthesias / dysesthesias that are			
	disabling or life-threatening			
Pharyngo-laryngeal dysesthesias (investigator discretion used for grading): Grade 0 = none;				
Grade 1 = mild; Grade 2 = moderate; Grade 3 = severe				

Overdose

There is no known antidote available in case of TAS-102 overdose. Overdose should be managed aggressively with close monitoring and administration of prophylactic and symptomatic therapies to prevent or correct potential side effects.

Dosage Forms and Strengths

TAS-102 (15 mg trifluridine/7.065 mg tipiracil hydrochloride) is a white, film-coated tablet. Tablets can be printed or unprinted.

TAS-102 (20 mg trifluridine/9.42 mg tipiracil) is a pale red, film-coated tablet Tablets can be printed or unprinted.

TAS 102 tablets are supplied by way of a pouch containing a 20ct blister card.

9.0 ANCILLARY TREATMENT/SUPPORTIVE CARE

9.1 Concomitant medications and therapies.

All concomitant medications and treatments must be recorded from the time the participant signs the ICF until 28 days after the last dose of study treatment.

Caution is required when using drugs that are human thymidine kinase substrates, e.g., zidovudine. Such drugs, if used concomitantly with TAS-102, may compete with the effector, trifluridine, for activation via thymidine kinases. Therefore, when using antiviral drugs that are human thymidine kinase substrates, monitor for possible decreased efficacy of the antiviral agent, and consider switching to an alternative antiviral agent that is not a human thymidine kinase substrate, such as lamivudine, zalcitabine, didanosine and abacavir.

- Trifluridine is a substrate of thymidine phosphorylase, and is not metabolized by cytochrome P450 (CYP) enzyme.
- Tipiracil is not metabolized in either human liver or hepatocytes.

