6.0 PROTOCOL TREATMENT

Therapy: Study schema is summarized in Section 2.3. Patients are initially treated with 25 Gy in five fractions of 5 Gy conformal pelvic radiation. Radiation is to be started within 3 weeks of registration. TASOX should be commenced within 3 weeks of radiation completion. Patients are treated with 6 x 14 day cycles of TASOX. Within 4 weeks of the end of cycle #6 of TASOX patients undergo re-staging. Surgery should be performed within 4 weeks AFTER day 14, cycle#6 of TASOX, i.e., 28 days after day 14, cycle 6.

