12.0 POST-OPERATIVE THERAPY

Recommendations for post-operative systemic therapy are not protocol specified and are according to recommendation of the investigator based clinical evidence and NCCN guidelines. Post-operative FOLFOX or 5-Fluorouracil plus Leucovorin/Capecitabine may be recommend taking into consideration clinical and pathologic stage and patient preference.

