14.2 Sample Size

In table 2, the NAR scores of comparable patients enrolled in the phase III R04 study (27) and treated with long-course chemoradiation are presented (personal communications [name]). Patients with cT3N0 tumors and similar in stage to those to be enrolled in the proposed concept achieved a NAR score of 14.59 (SD 13.41). Prospective data suggests a 5.8 reduction in NAR score would be a clinically significant improvement in long terms outcomes. (15) For declared target 5.8 NAR reduction from 14.59 to 8.79 a sample size of 24 patients would be required, one-sided alpha=0.1 and beta=0.2 (Power 80.2%). Assuming an ineligibility rate of 10%, the final sample size is **27**.

Patients who pursue a course of watch and wait remain evaluable on study and will be classified as having a ypT0N0 response for the purposes of the NAR score if they do not proceed to TME surgery within 24 months of cycle 6 day 14.

R04 similar subgroup	Inclusion	Preoperative Therapy	Ν	ypT0N0 Rate	NAR Score
	cT1-3 cN any	LRT 50.4/25 plus Fluorouracil	631	18.4%	15.77 SD 14.17
	cT3 Non-Low	"	402	18.4%	16.05 SD 14.32
	cT3 cN0 Non-Low	"	293	20.2%	14.59 SD 13.41

Table 12. pCR and NAR scores in R04 patients.

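### Treatment recording stops before the NAR score is fixed, and the watch-and-wait rule codes ypT0N0 at 24 months even if non-protocol anticancer treatment was given

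*Combined protocol and SAP*

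**What the plan says.** - **Recording.** Section 9.1: "All concomitant medications and treatments must be recorded from the time the participant signs the ICF until 28 days after the last dose of study" therapy. Section 9 gives a drug-interaction caution and permits supportive care. It contains no rule on other anticancer treatment.
- **Last dose.** Section 6.2.1: "Study medication should be taken on Days 1-5" of each 14-day cycle. Oxaliplatin is given on day 1 (section 6.3).
- **Time of TME.** Section 6.4 says surgery "is to be done within 10 weeks of completion of cycle #6 of chemotherapy with TASOX", and note 9 of section 4.0 also gives 10 weeks. Section 6.0 says: "Surgery should be performed within 4 weeks AFTER day 14, cycle#6 of TASOX".
- **Watch-and-wait.** Complete or near-complete clinical responders may defer surgery. Section 14.2 gives the rule, with the period in months counted from cycle 6 day 14: such patients "will be classified as having a ypT0N0 response for the purposes of the NAR score if they do not proceed to TME surgery within 24". Note 12 of section 4.0 and section 6.4 give the same rule. The only condition is the absence of TME.
- **Early stopping.** Table 7 in section 8.1.3: "If ANC remains less than 1.2 after 4 weeks, discontinue treatment". Table 8 has the matching rule for platelets.
- **Other therapy.** Section 12 begins: "Recommendations for post-operative systemic therapy are not protocol specified". It concerns treatment after the specimen has been taken, which cannot alter the NAR. Exclusion 3.2.5 concerns chemotherapy before registration.
- **Analysis.** Section 14 has no rule for non-protocol anticancer treatment given before the NAR is fixed.

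**The concern.** The primary endpoint is meant to measure what short-course radiation plus six cycles of TASOX achieves. In watch-and-wait, the stated rule can give a wrong score. Near-complete responders may still have disease. If residual or recurrent disease is treated within the 24 months by any means other than TME, the patient is still entered as ypT0N0. The error always lowers the NAR, which is the direction of success. The comparison is with a fixed historical mean, so no concurrent arm offsets it.

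The record that would expose the problem closes early. Section 9.1 stops 28 days after the last dose, and the schedule of tests in section 4.0 has no watch-and-wait visit. A weaker form of the same gap exists before TME: a specimen obtained after other treatment is scored like any other, and even treatment captured within the 28 days is not used by any analysis rule.

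**Working it through.** **1. The plan's own figure.** Inputs from section 14.2: null mean 14.59, SD 13.41, reduction 5.8, one-sided alpha 0.10, power 80.2%, n = 24, total 27. Section 14.2 names no test, so I assume a one-sample comparison of a mean with a fixed value (normal approximation).

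- n = [13.41 × (1.2816 + 0.8416) / 5.8]² = 24.10.
- Power at n = 24 is 79.9%, close to the stated 80.2%.
- 24 / 0.9 = 26.7, rounded up to 27.
- The standard error is 13.41/√24 = 2.737, so success needs a mean at or below 14.59 − 1.2816 × 2.737 = 11.08, which is 3.51 below the null.

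**2. Unrecorded time after a full course.** The last TAS-102 dose is on cycle 6 day 5, and completion of cycle 6 is taken as day 14.

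- Recording ends on day 5 + 28 = day 33, which is 19 days after day 14.
- To TME under the 4-week wording: 28 − 19 = 9 days.
- To TME under the 10-week wording: 70 − 19 = 51 days.
- Watch-and-wait: 730 − 19 = 711 of about 730 days (97%).

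**3. Early stoppers.** The 28 days run from each patient's own last dose. If counts stay low after a cycle, recording closes by day 33 of that cycle. The next cycle was due on day 15, and a 4-week hold ends about day 43. Recording therefore closes about 10 days before the patient is taken off treatment under Tables 7 and 8.

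**4. Score values.** From section 1.3, NAR = [5pN − 3(cT − pT) + 12]² / 9.61. For cT3:

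| Stage | Calculation | NAR | Excess over ypT0N0 | Shift in the mean of 24 |
|---|---|---|---|---|
| ypT0N0 | 3²/9.61 | 0.94 | – | – |
| ypT2N0 | 9²/9.61 | 8.43 | 7.49 | 0.31 |
| ypT3N0 | 12²/9.61 | 14.98 | 14.05 | 0.59 |
| ypT3N1 | 17²/9.61 | 30.07 | 29.14 | 1.21 |

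The ypT3N0 shift is 0.59/5.8 = 10% of the target reduction and 0.59/3.51 = 17% of the distance to the success limit. The ypT3N1 shift is 21% of the target.

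**5. Effect on the false-positive rate.** Suppose the true mean is 14.59 and k of 24 cT3 patients are scored 0.94 in place of the stage shown, with the SD unchanged. The rate is Φ(−1.2816 + k × shift/2.737), against a nominal 0.10:

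| k | From ypT2N0 | From ypT3N0 |
|---|---|---|
| 1 | 0.12 | 0.14 |
| 2 | 0.15 | 0.20 |
| 3 | 0.17 | 0.26 |

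The value of k is an assumption. The documents give no rate of non-protocol treatment.

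**The case against.** **Detectability before TME.** A reader might infer that patients given other treatment could never be identified. The documents do not support that for the pre-operative period. Section 4.0 requires a history at the pre-operative visit and an assessment at progression, withdrawal or removal. Section 15.0 monitors adherence to the treatment plan, source documents and deviations, and treatment inserted into the prescribed sequence of radiation, TASOX and TME should partly surface there. The argument has full force only in watch-and-wait.

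**The 51 days.** A reader might take this as the gap. It is the upper end, because section 6.0 gives a window that leaves 9 days.

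**Size.** The 0.6 to 1.2 points assume that the whole difference from ypT0N0 is at issue. For treatment given before TME, that means assuming a complete response. Table 12 shows ypT0N0 in only 18.4% to 20.2% of patients after fluorouracil chemoradiation, with mean NAR 14.59 to 16.05. Those are first-line data and only a guide, but they do not support complete response as the usual result. This point stands.

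**Cause.** A watch-and-wait patient who would have avoided TME anyway scores 0.94 with or without other treatment, so 711 unrecorded days measure missing information, not bias. That is correct. It does not rescue the rule, because treatment for residual or recurrent local disease is itself evidence against ypT0N0.

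**Remedy.** Scoring every treated patient as having no downstaging in the primary analysis would discard real specimens in favour of imaging stage, which Appendix I concedes is inexact. It could move a cT3N1 patient from 0.94 to 30.07, adding 1.21 to the mean. Analysing the observed specimen regardless of added treatment is a legitimate choice. That scoring belongs in a sensitivity analysis.

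**Conclusion.** The concern holds for the watch-and-wait rule together with the recording window. Followed as written, the plan scores a patient ypT0N0 at 24 months despite intervening anticancer treatment, and it requires no record that would show this. For cT3, each such patient who would otherwise be ypT3N0 lowers the mean of 24 by about 0.6, towards success. That figure credits the full difference to each patient and is an upper-bound illustration for that stage. The number of patients is unknown, so the false-positive rates above are conditional and are not a forecast.

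Before TME, the concern is limited to an unrecorded gap of 9 to 51 days after a full course, longer for early stoppers, and to the lack of an analysis rule. The documents do not support saying that these patients could not be found, or that the primary result is biased by a known amount.

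**What to change.** 1. **Section 9.1:** record all anticancer treatment (systemic, radiation and non-TME local procedures) until TME or, without TME, until TME status is determined at 24 months.
2. **Section 14.2, section 6.4 and note 12 of section 4.0:** state that a watch-and-wait patient who receives non-protocol anticancer treatment before 24 months is not automatically coded ypT0N0, but is scored from the disease stage documented at that treatment.
3. **Patients who reach TME after non-protocol treatment:** keep the observed specimen in the primary NAR and flag them.
4. **Sensitivity analysis:** score all affected patients as having no downstaging (pT = cT, pN = cN).
5. **Sections 6.0 and 6.4 and note 9 of section 4.0:** reconcile the 4-week and 10-week surgery windows, since they set the length of the pre-operative gap.

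These changes concern recording and scoring only. They restrict no treatment and leave the sample size of 24 (27 in total) unchanged. The cost is one treatment-history item at the 24-month check. That check is not a scheduled visit in section 4.0, but TME status must already be established then to apply the existing rule. The mean NAR may come out less favourable. The rule should be fixed before analysis, because treatment histories not collected prospectively may be hard to recover.
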